Preregistration on Clinicaltrials.gov

Project:

„Hypnosis Induction and Height Experience in VR - Control Group Comparison and Three Sessions“

Unique Protocol ID: 521/2019BO2

Description of the Hypotheses, Analyses and needed Sample Sizes

06.05.2024

1. Data collection. Have any data been collected for this study already?

No data has been collected for this study.

2. Hypothesis: What's the main question being asked or hypothesis being tested in this study?

- a. Do three sessions of VR therapy reduce the fear of heights in both groups?
 - i. We expect a decrease in fear of heights over the sessions.
 - ii. Fear of heights decreases over the three sessions, with the experimental group benefiting more from the sessions than the control group.
- b. The fear of heights increases less from after the last therapy session to the follow-up measurement after one week in the experimental group than in the control group.
- c. Does the anxiety experience curve change during the VR height confrontation over the three sessions in both groups?
 - i. We expect typical anxiety experience curves according to the habituation (linear increase in anxiety and quadratic decrease).
 - ii. We expect a decrease of the mean anxiety experience rating over the sessions.
 - iii. We expect that the anxiety experience curves rise less sharply with each session.
 - iv. We expect that the anxiety experience curves reach their turning point earlier with each session.
 - v. The experimental group has lower anxiety experience ratings across all sessions and rises (20 ascents during the height confrontation) compared to the control group.
- d. How does a person's suggestibility influence the perception and impact of the intervention?
 - i. More suggestible people show a greater reduction in anxiety over the three sessions than less suggestible people.
 - ii. The influence of suggestibility on the strength of reduction in anxiety over the three sessions is stronger in the experimental group than in the control group.
 - iii. Suggestibility and group affinity interact such that in the experimental group participants with higher suggestibility show a lower level of anxiety experience during the height confrontation than less suggestible participants, but in the control group higher suggestible participants exhibit greater anxiety experience during the height confrontation than less suggestible participants.

3. Analyses

The analyses are carried out using linear mixed models. Each model is tested with the car::Anova() function (model comparison Typ II ANOVA) in R to determine the significance of the individual effects. The model equations are written down below and the abbreviations used for the effects are explained.

grp: experimental vs. control group (enters model equation as factor: experimental

group is reference group)

sugg: suggestibility (enters model equation as linear predictor)

a. HIQ ~ grp + sess + grp:sess + (1 | id)

sess: baseline vs. post first session vs. post second session vs. post third session (enters model equation as factor)

For hypothesis a(i) we investigate the significance of sess.

For hypothesis a(ii) we investigate the significance of grp:sess.

b. HIQ ~ grp + sugg + mtp + sugg:mtp + grp:sugg + grp:mtp + grp:sugg:mtp + (1 | id)

mtp: measurement time point, baseline vs. post third session (enters model equation as factor)

For hypothesis d(i) we investigate the significance of sugg:mtp.

For hypothesis d(ii) we investigate the significance of grp:sugg:mtp.

c. HIQ ~ grp + mtp + grp:mtp + (1 | id)

mtp: measurement time point, post third session vs. one-week follow-up (enters model equation as factor)

For hypothesis b we investigate the significance of grp:mtp.

d. fear ~ grp + sugg + sess + rise + rise^2 + grp:sugg + sess:rise + sess:rise^2 + (rise + rise^2 | id)

sess: first session vs. second session vs. third session (enters as linear predictor)

rise: 20 rises during each of the three sessions, these are entered as a centered variable into the model equation (centered at total mean)

For hypothesis c(i) we investigate the significance of rise and rise^2.

For hypothesis c(ii) we investigate the significance of sess.

For hypothesis c(iii) we investigate the significance of sess:rise.

For hypothesis c(iv) we investigate the significance of sess:rise^2.

For hypothesis c(v) we investigate the significance of grp.

For hypothesis d(iii) we investigate the significance of grp:sugg.

4. Sample Size

- a. Analysis a needs 56 participants to achieve a Power of 80% for the effects of interest.

- b. Analysis **b** needs 92 participants to achieve a Power of 80% for the effects of interest.
- c. Analysis **c** needs 60 participants to achieve a Power of 80% for the effects of interest.
- d. Analysis **d** needs 50 participants to achieve a Power of 80% for the effects of interest.

In order to prevent insufficient Power due to drop-outs, about 10% more participants should be surveyed. A total of 100 participants should therefore be surveyed (50 per group). If it is not possible to survey 100 participants, some of the analyses mentioned above can also be carried out with fewer participants and (as indicated) still enough Power.

5. Exploratory Analyses

- a. Exploratory Relationships:
 - i. More suggestible people report a higher perceived presence in the VR environment than less suggestible people (in both groups).
 - 1. Correlation test (correlation between suggestibility and average experience of presence)
 - ii. More suggestible persons in the experimental group report a higher subjective trance depth than less suggestible persons in the experimental group.
 - 1. Correlation test (correlation between suggestibility and mean trance depth of the experimental group)
- b. Exploratory Analyses:
 - i. We expect a reduction in fear of heights after each session.
 - 1. $\text{HIQ} \sim \text{grp} + \text{mtp} + \text{grp:mtp} + (1 | \text{id})$ (for all sessions)
 - a. mtp: measurement time point, pre vs. post per session
 - ii. We expect that the experimental group shows a lower level of fear of heights in the one-week follow-up than in the pre-measurement of the second session (one-week follow-up after one session). (no investigation of the control group)
 - 1. $\text{HIQ} \sim \text{follow} + (1 | \text{id})$
 - a. follow: pre second session vs. one-week follow-up
 - iii. We also plan to look at how many subjects in the experimental group continue to report a fear of heights below the cut-off for inclusion in the study (HIQ Score > 29) after three months.
- c. Checks:
 - i. We expect no difference in suggestibility between the groups.
 - 1. $\text{sugg} \sim \text{grp} + (1 | \text{id})$
 - ii. We expect no influence of suggestibility on the initial extent of fear of heights
 - 1. $\text{HIQ} \sim \text{sugg} + (1 | \text{id})$
 - iii. We expect no difference in the initial extent of fear of heights between the two groups.
 - 1. $\text{HIQ} \sim \text{grp} + (1 | \text{id})$

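### The test statistic behind `car::Anova()` is not fixed; the function's default on mixed models is a Wald chi-square, slightly liberal for terms with about as many degrees of freedom as persons

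*SAP*

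**What the plan says.** Section 3 (Analyses) opens with the model class, "The analyses are carried out using linear mixed models", and then gives one testing rule for all four models: "Each model is tested with the car::Anova() function (model comparison Typ II ANOVA"). Its stated purpose is "to determine the significance of the individual effects". The SAP does not name the fitting package, the test statistic, a denominator degrees-of-freedom method, the choice between REML and ML, or the significance level.

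The largest model is d: "fear ~ grp + sugg + sess + rise + rise^2 + grp:sugg + sess:rise + sess:rise^2 + (rise + rise^2 | id"). Two hypotheses rest on its purely between-person terms: "For hypothesis c(v) we investigate the significance of grp" and "For hypothesis d(iii) we investigate the significance of grp:sugg".

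Section 4 (Sample Size) gives 56, 92, 60 and 50 participants for analyses a, b, c and d, and a target of 100 in total. It adds that if 100 cannot be reached, "some of the analyses mentioned above can also be carried out with fewer participants".

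**The concern.** The label and the function point to different tests. A reader of the words model comparison would expect a likelihood-ratio test between two fits, and a reader of the word ANOVA would expect an F test. Called without further arguments on an lme4 fit, `car::Anova()` gives neither. It computes Wald chi-square statistics from a single fit and refers them to a distribution that treats the variance components as known.

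That makes little difference where a term is tested against thousands of residual degrees of freedom. It makes some difference where the effective degrees of freedom are close to the number of persons, however many ratings each person gives. The type I error is then a little above nominal, most of all in the smaller samples that section 4 accepts. A preregistration should also settle in advance which of several available tests decides a hypothesis.

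**Working it through.** **Inputs from the SAP.** `car::Anova()`, Type II; the four model equations; N of 56, 92, 60 and 50 for analyses a to d; target N of 100.

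**Assumptions.** Two-sided alpha of 0.05 (not stated); lme4 fits with REML (lme4 inferred from the `(1 | id)` notation); default test statistic; balanced data. The SAP's sample sizes cannot be reproduced, because it gives no effect sizes, variance components, alpha or power method.

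**Step 1: what the function does.** For lme4 fits the argument is `test.statistic = c('Chisq', 'F')`, so chi-square is the default. Run on a fit of model d, the output is headed Type II Wald chisquare tests and shows no denominator degrees of freedom. The F version must be requested. In an example with 60 persons and two time points it gave 58 Kenward-Roger degrees of freedom, that is N−2.

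**Step 2: one-df terms.** True error = P(|t_df| > 1.960).

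| Term | N | df | True error |
|---|---|---|---|
| d: `grp`, `grp:sugg` | 50 | 50−4 = 46 | 5.61% |
| d: `grp`, `grp:sugg` | 100 | 100−4 = 96 | 5.29% |
| d: `rise`, `rise^2` (random slopes) | 50 | 50−1 = 49 | 5.57% |
| d: `rise`, `rise^2` (random slopes) | 100 | 100−1 = 99 | 5.28% |
| b: `sugg:mtp`, `grp:sugg:mtp` | 92 | 92−4 = 88 | 5.32% |
| c: `grp:mtp` | 60 | 60−2 = 58 | 5.48% |
| c: `grp:mtp` | 100 | 100−2 = 98 | 5.28% |

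The 4 in models b and d counts the person-level parameters: intercept, `grp`, `sugg` and `grp:sugg`.

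**Step 3: three-df terms in model a** (`sess`, `grp:sess`). The 5% chi-square limit is 7.815, so true error = P(F(3, 3(N−2)) > 7.815/3 = 2.605). N=56: 162 denominator df, 5.37%. N=100: 294 df, 5.20%.

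**Step 4: terms not affected.** Model d has random terms only for the intercept, `rise` and `rise^2`. Under that model, `sess`, `sess:rise` and `sess:rise^2` are tested against residual error. At N=50 there are up to 50 × 3 × 20 = 3,000 ratings, or roughly 2,800 residual df, which gives 5.01%.

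**Step 5: simulation.** For `grp` and `grp:sugg`, 200,000 simulated person-level data sets gave 5.56% and 5.63% at N=50, and 5.38% and 5.26% at N=100, in agreement with step 2. A direct simulation with `car::Anova()` on a two-time-point model (1,500 runs, Monte Carlo standard error about 0.6 points) gave 4.6% to 5.9%. This is compatible, but too noisy to resolve differences of this size.

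**Step 6: the literal label.** A likelihood-ratio comparison of ML fits rejects when |t| > √(df × (exp(1.960²/N) − 1)). For the between-person terms of model d this limit is 1.917 at N=50 and 1.939 at N=100, giving true errors of about 6.2% and 5.5%.

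**Step 7: what would change.** The t limit is 2.013 at 46 df and 1.985 at 96 df. Only Wald p-values between about 0.044 and 0.050 (46 df), or 0.047 and 0.050 (96 df), would change verdict.

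**The case against.** The strongest reply is that the effect is almost too small to matter. At the target of 100 the excess is about 0.3 points or less, and the 5.6% figure belongs to model d at N=50 alone. This is correct and sets the severity.

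A second reply is that the SAP does not actually prescribe the Wald test. It names neither the package nor the argument, so the F version is not excluded, and Type II tests can loosely be described as comparing models under the marginality principle. This also stands in part: the wording is imprecise rather than plainly false, and use of the default is an inference. But the deciding test is then left open. The literal alternative, a likelihood-ratio comparison, would be more liberal than Wald (step 6), so it does not rescue the plan.

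Three stronger readings are tempting and are not supported:

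- **Every confirmatory test is inflated.** Step 4 shows that hypotheses c(ii), c(iii) and c(iv) are essentially unaffected under the fitted model.
- **Only between-person effects are inflated.** The time contrasts in models b and c are within-person, yet with two time points they too have only about N−2 to N−4 degrees of freedom. `rise` and `rise^2` are affected through their random slopes.
- **An exact test is available.** Kenward-Roger is in general an approximation, and with unbalanced data after drop-out and three random terms in model d it should not be called exact.

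**Conclusion.** The point holds as a minor one. The SAP leaves the test statistic unstated and attaches a label that does not describe the function's default on lme4 fits. If that default is used, the tests resting on roughly as many degrees of freedom as there are persons run at about 5.3% to 5.6% instead of 5%. The model a tests run at 5.2% to 5.4%.

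These figures depend on alpha of 0.05, lme4 with REML, the default statistic and balanced data, none of which the SAP states. A reader might infer that the planned inference is invalid. It is not: only results just under the significance limit could be affected.

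**What to change.** In section 3, specify `car::Anova(model, type = 2, test.statistic = 'F')` on REML fits, with Kenward-Roger degrees of freedom. For the large model d, Satterthwaite degrees of freedom (for example through lmerTest) are a workable alternative. Replace the words model comparison with this description, and state alpha and sidedness.

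The cost is one function argument, one or two sentences and a longer run time for model d. P-values become marginally larger. If the stated 80% power came from a normal approximation, which the SAP does not say, power for one-df tests against the t reference would be 78.3% at N=50 (46 df), 78.7% at N=60 (58 df) and 79.1% at N=92 (88 df).

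### Analysis a leaves suggestibility out of the a(ii) group comparison, although d(i) expects it to explain HIQ reduction over the same sessions; a minor gain in efficiency and robustness is available

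*SAP*

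**What the plan says.** SAP section 3, analysis a, models HIQ at baseline and after each of three sessions as "HIQ ~ grp + sess + grp:sess + (1 | id"). It adds: "For hypothesis a(ii) we investigate the significance of grp:sess". Suggestibility does not appear.

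The trial collects suggestibility and uses it as a linear predictor in analyses b and d. Hypothesis d(i) in section 2 reads: "More suggestible people show a greater reduction in anxiety over the three sessions than less suggestible people". It is tested in analysis b through sugg:mtp, with HIQ at baseline and post third session, which are the first and last time points of analysis a. Hypothesis d(ii) expects that influence to be stronger in the experimental group.

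Section 5c(i) adds a balance check, "We expect no difference in suggestibility between the groups", and says nothing about what follows if the check fails. Section 5c(ii) expects suggestibility to be unrelated to initial HIQ.

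Analysis c, for hypothesis b, also omits suggestibility: "HIQ ~ grp + mtp + grp:mtp + (1 | id"). Its time points are post third session and one-week follow-up.

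Section 4 gives the numbers for 80% power: 56 for analysis a, 92 for b and 60 for c. The target is 100 in total, including about 10% for drop-out, and section 4 allows some analyses to go ahead with fewer.

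**The concern.** The plan names a predictor of HIQ reduction over the sessions, measures it, and leaves it out of the model that compares HIQ reduction between groups. Two things follow if d(i) is true.

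- **Precision.** The part of each participant's change that suggestibility explains is counted as residual variation in the grp:sess test.
- **Imbalance.** If the groups differ in suggestibility, part of that difference appears as a group-by-session effect. A significance test of balance is a weak guard, because an imbalance large enough to matter can pass it at these sample sizes. With no rule attached, any adjustment would be decided after seeing the data.

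The SAP states that no data have been collected, so the choice can still be fixed in advance.

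**Working it through.** **1. The plan's own figure.** The 56 for analysis a cannot be rebuilt, because alpha, effect sizes, standard deviations and within-person correlation are not given. I take it as given and assume alpha 0.05, complete data and equal groups. The grp:sess test has 3 and 3 × (56 − 2) = 162 degrees of freedom. The noncentrality that gives 80% power is 11.17.

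**2. Which term helps.** grp:sess is a within-person contrast, and stable differences between people go into the random intercept. In one simulated data set (56 people, four time points, a 0.4 SD group difference in suggestibility built into the simulation) the baseline-to-last group contrast was:

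| Model | Estimate | SE |
|---|---|---|
| no suggestibility | −4.21 | 2.22 |
| + sugg | −4.21 | 2.22 |
| + sugg + sugg:sess | −3.23 | 2.17 |

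Only the interaction with session does anything.

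**3. An assumed strength for suggestibility.** As a rough guide, the simple correlation detectable with 80% power at N = 92, two-sided 5%, is tanh[(1.960 + 0.842)/√89] = 0.29, so r² = 0.083. This is an assumption. Section 4 gives 92 for both effects of interest in analysis b and does not say whether sugg:mtp or grp:sugg:mtp sets it.

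**4. From change score to the error of analysis a.** The 8.3% refers to baseline-to-post-third change. The random-intercept model tests grp:sess against a residual pooled over three within-person contrasts. Set the variance of that change to 1. The residual variance per measurement is (1 − 0.083)/2 = 0.458. Let w be the suggestibility effect at each time point as a fraction of its final size.

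- Linear build-up, w = 0, 1/3, 2/3, 1: Σ(w − w̄)²/3 = 0.185. Share = 0.083 × 0.185/(0.458 + 0.083 × 0.185) = 3.3%.
- Step after session one, w = 0, 1, 1, 1: Σ(w − w̄)²/3 = 0.25. Share = 0.083 × 0.25/(0.458 + 0.083 × 0.25) = 4.3%.
- Ceiling: the full 8.3%.

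**5. Power after adding sugg and sugg:sess.** Noncentrality = 11.17 × (N/56)/(1 − share)/(1 + 1/(N − 3)). The last factor is the average cost of collinearity with group. Error degrees of freedom fall by 3. N = 90 is 100 less 10%.

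| Share removed | N = 56 | N = 90 |
|---|---|---|
| unadjusted | 80.0% | 95.6% |
| 0 | 79.2% | 95.4% |
| 3.3% | 80.6% | 96.0% |
| 4.3% | 81.1% | 96.2% |
| 8.3% | 82.9% | 96.8% |

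This formula treats the omitted variation as spread evenly over the three contrasts. I therefore also simulated the within-person F test directly at r = 0.29. Both the suggestibility and the group effect were varied over linear, early-step and last-session-only patterns. The gain was 0.6 to 2.2 points at N = 56 and 0.3 to 1.3 points at N = 90. It was largest when both effects followed the same step pattern.

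**6. Imbalance.** Take r = 0.29 and a 0.4 SD group difference in suggestibility. The unadjusted contrast shifts by 0.29 × 0.4 = 0.12 SD of change. With 28 per group its standard error is √(2/28) = 0.267 SD, so the shift is 0.43 standard errors, or 0.43/2.80 = 15% of the effect detectable with 80% power. The same imbalance gives check 5c(i) a z of 0.4/0.267 = 1.5, which is not significant. Under random allocation an imbalance at least this large in either direction occurs about 13% of the time at N = 56 and 5% at N = 100 (z = 0.4/0.2 = 2.0).

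**The case against.** The strongest reply is that nothing here is wrong. The unadjusted grp:sess test is valid, and choosing covariates is a matter of efficiency. That stands: a reader might infer that a(ii) as planned is biased or invalid, and the document does not support that.

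At the planned size the gain is small, because the plan's own figures already put power for analysis a at about 95% or more with 90 completers. That also stands. The larger gain belongs to the smaller sample that section 4 allows for.

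A reader might take the 8% as the plan's figure and expect power to rise from 80% to 83.5%. Neither holds. The 92 may be set by the three-way term, and a share of the first-to-last change is a smaller share of the pooled residual.

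A reader might also call the adjustment free. It costs three degrees of freedom, and participants without a suggestibility score would drop out of the model.

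It is tempting to extend the point to analysis c. Hypothesis d(i) concerns the three sessions only, whereas analysis c is defined by "mtp: measurement time point, post third session vs. one-week follow-up (enters model equation as factor". No hypothesis links suggestibility to that later change, so any explained share there would be invented.

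Analysis b already contains grp:mtp beside sugg:mtp for baseline and post third session, so a related adjusted test will be in the output. But the plan does not assign that term to a(ii), and it uses two of the four time points.

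Finally, d(ii) expects a three-way interaction, which the proposed model leaves out. That is acceptable for an average group comparison, since d(ii) has its own test in analysis b. If a three-way term were added, centring would be needed for grp:sess to refer to average suggestibility.

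**Conclusion.** The point holds for analysis a, as a minor efficiency and robustness improvement. The plan's own d(i) makes suggestibility a covariate for the change that a(ii) compares, and the model omits it.

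With a correlation of about 0.29 between suggestibility and baseline-to-post-third change, the gain for a(ii) is roughly 1 to 3 power points at N = 56, with 3 as the ceiling, and about 1 point at 90 completers. If suggestibility explains nothing, the loss is about 0.8 points at N = 56 and 0.2 to 0.3 at 90. Protection against imbalance is the better argument at small N: a 0.4 SD difference would shift the contrast by about 15% of the detectable effect and would usually pass the balance check.

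These sizes rest on alpha 0.05, complete data, equal groups and the assumed correlation. The document does not describe allocation, so calling an imbalance a chance one is also an assumption. For analysis c the same change is at most optional.

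**What to change.** In SAP section 3, write analysis a as

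`HIQ ~ grp + sess + grp:sess + sugg + sugg:sess + (1 | id)`

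with sugg centred at its overall mean. State that a(ii) is read from grp:sess in this model whatever check 5c(i) shows. Adding sugg without sugg:sess would not serve the purpose. Say also how participants without a suggestibility score are handled, and keep the unadjusted model as a supporting analysis if wished.

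Analysis c can stay as it is.

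The cost is a wording change, made before data collection, with a covariate the trial already collects. In the analysis it costs three degrees of freedom and requires complete suggestibility scores.

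### Analyses a and b test group effects on HIQ as unadjusted change from baseline; adjusting for baseline HIQ would be more precise, chiefly for hypothesis d(ii)

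*SAP*

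**What the plan says.** Analysis a in SAP section 3 is "HIQ ~ grp + sess + grp:sess + (1 | id". Its time factor is defined as "sess: baseline vs. post first session vs. post second session vs. post third session (enters model equation as factor", so baseline is an outcome level with its own free group difference. The decision rule is "For hypothesis a(ii) we investigate the significance of grp:sess".

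Analysis b is "HIQ ~ grp + sugg + mtp + sugg:mtp + grp:sugg + grp:mtp + grp:sugg:mtp + (1 | id", with two time points, baseline and after the third session. Hypothesis d(ii) is judged by the three-way term. Neither model has a baseline covariate or a baseline mean shared by the groups. On testing, the section says "Each model is tested with the car::Anova() function (model comparison Typ II ANOVA) in R".

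Section 5, Checks iii, states "We expect no difference in the initial extent of fear of heights between the two groups". Checks ii expects suggestibility to be unrelated to initial HIQ.

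On size, section 4 says "Analysis a needs 56 participants to achieve a Power of 80% for the effects of interest" and gives 92 for analysis b. It adds about 10% for drop-out and concludes "A total of 100 participants should therefore be surveyed (50 per group". It also allows some analyses to go ahead with fewer participants if 100 cannot be reached.

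**The concern.** The plan spends precision on estimating a baseline group difference that it expects to be zero. A change score carries all of the baseline noise, and a chance imbalance at baseline passes straight into the estimated group effect. A covariate removes the part of that noise which baseline predicts, using data the trial collects anyway.

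Hypotheses a(ii) and d(ii) are the HIQ questions that set the experimental group against the control group from baseline to the end of treatment, so their precision matters. Analysis b also has the largest sample size requirement, and therefore the least room.

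**Working it through.** **Inputs.** From the SAP: 56 participants for 80% power in analysis a, 92 for analysis b, 100 planned in two equal groups, about 10% for drop-out. Not in the SAP, so assumed: two-sided alpha 0.05; rho from 0.5 to 0.8 for the main figures; equal variances and equal correlations across time points; complete data. The 56 and 92 cannot be reproduced, because no effect size, SD or correlation is given. They serve as anchors: the effect is set so that the planned test has exactly 80% power at that number.

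**One contrast.** With outcome variance 1, the change from baseline has variance 2(1 − rho), and the post value given baseline has variance 1 − rho². The ratio of adjusted to change is (1+rho)/2, which is 0.75, 0.85 and 0.90 at rho 0.5, 0.7 and 0.8.

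**Hypothesis a(ii), 3 df.** Power of 80% needs a noncentrality of 10.90. The three changes have covariance (1 − rho)(I + J), and the three post values given baseline have (1 − rho)(I + rho·J), where J is the matrix of ones. For a group effect growing as 1/3, 2/3, 1:

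- change: information is proportional to 14/9 − 4/4 = 0.556;
- adjusted: 14/9 − 4·rho/(1 + 3·rho) = 0.756, 0.652 and 0.614 at rho 0.5, 0.7 and 0.8.

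The information ratios are 1.36, 1.17 and 1.11. At N = 56 the noncentrality becomes 14.83, 12.80 and 12.06. At other N it scales with N/56.

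| N | Planned test | Adjusted, rho 0.5 | rho 0.7 | rho 0.8 |
|---|---|---|---|---|
| 56 | 80.0% | 91.4% | 86.5% | 84.2% |
| 90 | 95.4% | 99.1% | 97.8% | 97.1% |
| 100 | 97.2% | 99.6% | 98.8% | 98.3% |

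Simulation with 5,000 runs per setting at N = 56 agrees: 79.9% against 91.0% at rho 0.5, and 79.9% against 84.4% at rho 0.8. Under the null, at rho 0.6, rejection was 5.4% (planned) and 6.1% (adjusted), so only a small part of the gain could come from test size.

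The effect pattern matters. At N = 56 a constant group effect gives 95.3%, 89.8% and 86.6% after adjustment. An effect in the last session only gives 82.7%, 81.4% and 80.8%.

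**Hypothesis d(ii), 1-df normal approximation.** With two time points, the three-way term is the group-by-suggestibility interaction on change. Power of 80% at 92 means a standardised effect of 2.80. One hundred less 10% leaves 90, where it is 2.80 × √(90/92) = 2.77, or 79.1% power. Dividing by the square root of the variance ratio gives:

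| rho | Ratio | Standardised effect at 90 | Power at 90 | N for 80% (92 × ratio) |
|---|---|---|---|---|
| 0.5 | 0.75 | 3.20 | 89.2% | 69 |
| 0.7 | 0.85 | 3.01 | 85.2% | 78.2, so 79 |
| 0.8 | 0.90 | 2.92 | 83.2% | 82.8, so 83 |

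**Unequal variances.** If baseline SD is k times post SD, the ratio is (1 − rho²)/(1 + k² − 2·rho·k). At k = 0.8 it is 0.89, 0.98 and 1.00 at rho 0.5, 0.7 and 0.8, and power for d(ii) at 90 is 83.5%, 79.9% and 79.1%. At k = 1.2 the gain is larger than with equal variances.

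**The case against.** The strongest reply is that nothing here is an error. Hypothesis a(ii) is worded as a difference in decrease, and a group-by-session term tests exactly that. This stands: the point is about efficiency.

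A reader might infer that a(ii) is underpowered or biased. The SAP does not support either. Its own 56 lies well below the 100 planned, and on that anchor the planned test has 95 to 97% power with 90 to 100 participants. For a(ii) the loss matters mainly if recruitment falls towards 56, which section 4 allows for.

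A reader might also credit adjustment with the whole gain from replacing the 3-df test by one adjusted contrast after the third session, which has 92 to 96% power against 80% for rho 0.7 down to 0.4. That mixes two changes. With a linear effect, an unadjusted 1-df contrast already has 88% (noncentrality 10.90 × 0.9). Such a contrast also ignores sessions 1 and 2. For a constant or last-session-only effect it has less power than the planned test once rho exceeds about 0.85.

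Two further reservations stand. The inclusion cut-off on HIQ may narrow the baseline spread, which shrinks the gain and can remove it. The SAP also does not say how participants are allocated. Without random allocation, adjusted and change analyses can estimate different things, and Checks iii is an expectation to be tested, not a guarantee.

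**Conclusion.** The concern holds as a precision weakness in two valid tests. For a(ii) the gain from adjustment is about 4 to 11 points at N = 56 with a linear effect and rho between 0.8 and 0.5, but only about 1 to 4 points at the planned size. For d(ii) it is more useful: 90 completers fall just short of the 92 needed, and adjustment lifts power from about 79% to between 83% and 89% over the same range.

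The direction is secure: for rho between 0 and 1, equal variances and comparable groups, the adjusted test is never less informative, whatever the effect pattern. The size is not secure. It rests on an assumed rho, on equal variances, on an assumed effect pattern for a(ii), and on taking the SAP's 56 and 92 at face value.

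**What to change.** - **a(ii):** model the three post-session HIQ values with baseline HIQ as covariate plus group, session, their interaction and a random intercept. Test the group and group-by-session terms jointly on 3 df, by comparing the models with and without both. This comparison must be written out, because the planned term-by-term table does not give it. Testing the interaction alone in this model would miss a constant group effect. An alternative is to keep baseline as an outcome, give both groups one baseline mean, and test the three post-session group differences jointly.
- **a(i):** keep the present four-level model, which needs baseline as a time point.
- **d(ii):** regress HIQ after the third session on baseline HIQ, group, suggestibility and group-by-suggestibility, and test that interaction.
- **Sensitivity:** report the present change analyses alongside, since the SAP does not state random allocation.

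The cost is SAP wording and two added models. No new data are needed, and the SAP states that none had been collected when it was written, so at that point the change could be made before any result was seen.
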